**6.4.3 Inclusion of Women and Minorities:**

Refer to Section 6.14.4

**6.5 REGISTRATION PROCEDURES**

Not applicable; this is a single-institution trial

**6.6 TREATMENT PLAN**

Treatment will be administered on an outpatient basis. Reported adverse events and potential risks are described in Section 6.8.1. There will be no dose modifications for FES administration. No investigational or commercial agents or therapies other than those described below will be administered with the intent to treat the patient's malignancy.

**6.6.1 [F]FES Administration:**

FES will be administered in the PET imaging suite at the University of Washington Medical Center or at the Seattle Cancer Care Alliance (SCCA). The [F]FES for injection will be prepared as described in section 6.6.2, Study Procedures and Schedule of Events. Upon arrival, the patient will have an opportunity to have questions answered regarding the procedure. The patient will have an intravenous line placed prior to [F]FES administration. A dose of nominally 220 MBq (6 mCi with a range of 110 to 220 MBq = 3 to 6 mCi) of [F]FES will be administered intravenously by a physician. The injection will be infused over approximately 2 minutes and followed by a saline flush. The infusion and imaging procedure will be terminated in any patient who exhibits anaphylaxis, physical signs of significant hypotension, significant dyspnea or chest pain. We do not expect to observe any of these effects as no events have been reported in more than 300 scans performed with this compound at our institution to this date. The patient will then be allowed to rest comfortably in a prep room prior to being positioned in the PET scanner to commence the image acquisition at 60 +/- 10 minutes post FES injection.

Heart rate and blood pressure will be recorded pre- and post-FES dosing, and will continue to be monitored after injection until baseline is achieved.

Patients will be monitored for adverse events, potentially related to the administration of [F]FES, from the time of the initial injection to 10 hours post injection. Any adverse events will be recorded and reported according to FDA requirements (see section 6.8 Adverse Events).

## 6.6.2 Study Procedures and Schedule of Events

**6.6.2.a Initial visits prior to [F]FES PET:** Patients who are identified as potential candidates for the [F]FES PET study will be approached to explain the nature of the study and to obtain their written informed consent to be enrolled in the protocol. Heart rate and blood pressure will be recorded at the time of clinic visit where study is considered or at the time of consent. The patient will have a clinical FDG PET/CT scan if a recent FDG scan has not already been obtained. The FDG PET/CT scan should be obtained close to the time of FES PET/CT, typically within 14 days of the [F]FES PET/CT scan. An additional FDG PET/CT scan may be done as a research scan if the patient has undergone a recent PET scan at an outside institution or if they are unable to obtain a clinical PET scan as part of their clinical care. The research FDG PET/CT scan in this instance will be identical in procedure to a clinical FDG scan. The following additional patient data will be obtained: histological diagnosis, age at radiologic diagnosis, weight, gender, ECOG score and other treatment modalities used. Correlative radiology including CT, MRI, or bone scan, and laboratory tests measuring renal, blood and liver function will also be collected, typically for values within 30 days of the FES PET/CT scan. For patients referred from outside the UW health system, patient records, and biopsy material and imaging as necessary, will be reviewed to determine eligibility for the study.

**6.6.2.b Day of [F]FES PET/CT Scan:** After the FES injection and rest period (section 6.6.1), the patient will be positioned supine in the PET/CT scanner. A low dose CT scan (60 mA) will provide attenuation correction data using non-contrast CT. The PET image acquisition sequence will be the same as that used for clinical FDG scans. This consists of a torso survey series of five-minute images acquired over 15 cm survey fields of view (FOVs) extending from the base of the skull to the mid thigh (5 to 7 FOVs in total). The images will be corrected for radioactive decay of the tracer and normalized to the injected dose and body weight. This results in regional standardized uptake values (SUVs) whole-body image sets.

Prior to injection, a whole blood sample may be taken for determination of albumin, estradiol and testosterone levels, heart rate and blood pressure

will be recorded. A known quantity of nonradioactive FES will be added to plasma (from blood collected prior to injection) to determine binding to sex steroid binding protein (SBP). For patients in whom a second venous access line is feasible and has been placed, venous blood samples may be collected at 5, 20 and 60 minutes after injection of the [F]FES for metabolite analysis in selected patients. Heart rate and blood pressure will be measured after the FES injection.

**6.6.2.c After the [F]FES PET Scan:** A follow up phone call will be made by study staff within 24 hours after the FES PET scan to ask about any signs of adverse effects. Patients will typically start the selected hormone targeted therapy within 30 days of the FES PET scan. Patients who have started aromatase inhibitors prior to [F]FES PET will be permitted to enter the study, if an additional endocrine targeted treatment is planned.

**6.6.2.d** In patients who consent to optional biopsies, a baseline tumor sample will be obtained after completion of the baseline PET imaging but prior to starting the selected endocrine targeted therapy. Where available and medically appropriate, a clinical or research biopsy that involved sampling of a relevant lesion within 6 months prior to the enrollment may be utilized in place of the baseline optional biopsy.

In some patients undergoing biopsies, a whole blood sample will be collected prior to starting the therapy, to allow correlation of steroid hormone levels in serum and biopsy tissue.

**6.6.2.e Repeat FES PET scan and FDG PET scan :** Patients will undergo a second FES PET and FDG PET scan after starting endocrine targeted therapy to assess the effect of therapy on ER expression and estradiol binding to the receptor. Exact timing of the second FES and FDG scans, will depend upon the endocrine targeted regimen and dosing, but typically will be 1 – 12 weeks after starting therapy.

The repeat FDG PET may be omitted in patients on SERD therapies, where repeat FES PET is used primarily to evaluate residual ER availability rather than tumor response. This will be determined by requirements of the co-enrolling companion therapeutic protocol.

**6.6.2.f** In patients who consent to optional biopsies, an early response tumor sample will be obtained 1-12 weeks after starting the selected therapy. This biopsy should take place after completion of the repeat PET imaging and should target the same tumor site as the baseline biopsy. A whole blood sample may be drawn for correlation of steroid hormone levels in serum and biopsy tissue.

**6.6.2.g Week 1 to 20 years after [F]FES PET Scan:** Clinical follow-up will continue for up to 20 years, time of progression and date of death will be

recorded. For some patients, especially those receiving two endocrine-directed treatments, a third FES PET scan and additional research FDG PET scan may also be obtained 1-12 weeks after the second FES PET scan. For each patient, a maximum of 3 FES PET and 3 FDG PET scans would be done.

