## **6.10.2 [F]FES-PET Image Assessment**

### **6.10.2.a Summary of Assessment**

The FES PET scan will be assessed in multiple ways.

Qualitative FES uptake: all known disease sites positive vs. heterogeneous or absent FES uptake.

Quantitative FES uptake: SUVs in all lesions measured at baseline and repeat scan (and at third scan if indicated)

Quantitative change in FES uptake: percentage and SUV unit change in SUV between baseline and repeat FES PET scan

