#### **6.10.2.c Quantitative Assessment**

FES static survey images will undergo region of interest (ROI) analysis as follows: Lesion location will be identified using FES scans along with FDG scans with reference to CT or ultrasound. All patients will have undergone clinically motivated FDG PET scans for staging prior to FES imaging. CT, MRI, ultrasound or bone scan will be available on all patients with suspected metastatic disease. Although FES and FDG imaging will be performed on separate days, studies will be performed with the patient in the same position and images will be co-registered using common anatomic landmarks such as the lung outline, cardiac blood pool, liver contour, and body outline. In this way, regions can be drawn on the FDG images and transferred to the FES images for quantitative analysis which is important in identifying tumor locations, especially in ER-negative tumors which are not visualized on FES imaging. For each disease site, a set of 1.5 cm diameter regions on three adjacent planes with the highest lesion FES uptake will be drawn to determine maximal FES uptake. Up to the 10 largest sites seen on the static torso survey will be quantified. Partial-volume correction will not be used because only sites 1.5 cm or greater diameter will be included in quantitative analysis.

FES uptake will be quantified using the standard uptake value (SUV, defined below). For each site, we will record the average and maximum SUV within the ROI set for each site of disease.

For each subject, we will calculate the average and range of FES uptake values for active disease sites. The FES uptake will be compared with subsequent response to endocrine therapy and TTP.

FDG studies will also be quantified for uptake in a similar fashion. On FDG studies, simple SUVs will be generated using the average tissue activity over the imaging period, which are typically 45 and 75 minutes after injection. We will record the maximum FDG SUV for each site of

disease. Uptake at tumor sites using the standardized uptake value (SUV) is calculated as:

$$SUV = \frac{\overline{C}_t}{ID / wt}$$

where  $\overline{C}_t$  is the average tumor uptake after injection for the period of the static imaging for torso surveys (MBq/mL), ID is the injected dose (GBq) and wt is the patient's weight (kg). Note that either standard or metric units can be used to calculate SUV as long as only one type of unit is used for each calculation.

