**Table 6.2. Study Calendar.**

	Pre-Study	Imaging 1	Rx 1	Imaging 2 	Rx 2	Imaging 3 	Follow up
Informed Consent	X						
Demographics	X						
Pregnancy Test 	X						
Vital Signs 		X		X		X	
Research lab tests 		X		X		X	
ER, PgR, HER2 	X						
FDG PET/CT 	X			X		X	
[  F]FES injection and PET 		X		X		X	
Collect serum hormone levels 		X		X		X	
Adverse Event Evaluation		X (0-24hr)		X (0-24hr)		X (0-24hr)	
Optional tumor tissue biopsy and blood draw 		X		X			

 If patient is pre-menopausal, and birth control use is not confirmed

 Vital signs include heart rate and blood pressure

 Additional blood tests to measure hormone levels (e.g. estradiol, estrone, testosterone, DHT, SHBG) or other hormone related measures might be performed in some patients depending on the treatment regimen.

 Pathology results from primary or metastatic biopsy will be reviewed and additional pathology tests may be performed on some patients depending on the treatment regimen.

 FES PET/CT and FDG PET/CT will be done at 1-12 weeks after the Imaging 1 time point depending on the treatment regimen.

 Repeat FDG PET may be omitted in patients on SERD therapies.

 FES PET/CT and FDG PET/CT may be done at 1-12 weeks after the Imaging 2 time point depending on the treatment regimen.

 Optional blood sample for estradiol, estrone, follicle-stimulating hormone, sex hormone binding globulin, testosterone and free testosterone serum levels.

 In patients consented to optional biopsies, obtain metastatic or recurrent tumor tissue from an FDG and/or FES avid site after completion of PET imaging but prior to start of the endocrine targeted therapy. Repeat the biopsy from the same site after 1-12 weeks on treatment. (Where available and medically appropriate, a clinical or research biopsy that involved sampling of a relevant lesion within 6 months prior to the enrollment may be utilized in place of the baseline optional biopsy.) A blood draw done during the same time point will accompany some biopsies.

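### A lesion sampled at the study's own baseline biopsy is biopsied between the two scans being compared, and no analysis of the change in uptake is planned without it

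*Combined protocol and SAP*

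**What the plan says.** **Order of events.** Section 6.6.2.d states that in consenting patients "a baseline tumor sample will be obtained after completion of the baseline PET imaging but prior to starting the selected endocrine targeted therapy". Section 6.6.2.f then places the second biopsy at 1 to 12 weeks on therapy: "This biopsy should take place after completion of the repeat PET imaging and should target the same tumor site as the baseline biopsy". Footnote 9 of the study calendar (Table 6.2) gives the same order and directs the sampling: "obtain metastatic or recurrent tumor tissue from an FDG and/or FES avid site after completion of PET imaging".

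**Lesions measured.** Section 6.10.2.a lists "Quantitative FES uptake: SUVs in all lesions measured at baseline and repeat scan (and at third scan if indicated"). Section 6.10.2.c sets the limits: "Up to the 10 largest sites seen on the static torso survey will be quantified", and "only sites 1.5 cm or greater diameter will be included in quantitative analysis". It summarises each patient by the average and range over active sites, and records the maximum FDG SUV per site. Neither 6.10.2 nor 6.14.1 excludes, flags or separately analyses a biopsied site.

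**Outcome.** Section 6.12 makes the change in FES and FDG measures between serial scans the outcome. Section 6.14.1 expects a one-sample test of percent change in FES SUV, with no control group.

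**Exceptions.** A biopsy involving "sampling of a relevant lesion within 6 months prior to the enrollment may be utilized in place of the baseline optional biopsy" (6.6.2.d). On FDG: "The repeat FDG PET may be omitted in patients on SERD therapies" (6.6.2.e). Biopsy is optional and restricted to metastatic or recurrent disease (6.1, 6.10.3).

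**The concern.** Placing each biopsy after the scan of its own time point protects that scan. It does not protect the next one. The baseline biopsy falls inside the interval over which change is measured, and it is aimed at an avid lesion, which is likely to be one of the measured lesions. Section 6.6.2.e allows the repeat scan from one week after therapy starts, and no minimum interval between biopsy and repeat scan is given.

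The primary analysis reads the whole within-patient change as the effect of endocrine therapy. Without a control group, nothing in the planned analysis can separate a local effect of sampling from a drug effect. Exposure also varies between patients: those not biopsied have none, those with a substituted earlier biopsy were sampled before both scans, and those with the study biopsy were sampled between them. One qualifying lesion is enough for entry (6.4.1.c), so the biopsied lesion can be a patient's only measured site. A third scan (6.6.2.g) may in turn follow the second biopsy of the same site.

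**Working it through.** **Step 1: the plan's own power figures (6.14.1).** Inputs are n = 20, SD 25 percentage points (30 as the alternative) and level 0.05. Standard error = 25/√20 = 5.59 points. With the normal approximation, power = Φ(δ/SE − z), where δ is the distance from the null value:

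| Test | True change | SD | Stated | Normal approximation | Noncentral t |
|---|---|---|---|---|---|
| one-sided against 20% | 40% | 25 | 0.97 | 0.973 | 0.964 |
| one-sided against 20% | 35% | 25 | 0.85 | 0.850 | 0.827 |
| two-sided against 0 | 20% | 25 | 0.95 | 0.947 | 0.924 |
| two-sided against 0 | 20% | 30 | 0.85 | 0.846 | 0.807 |

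The stated figures reproduce with the normal approximation and are not in question here.

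**Step 2: is the sampled lesion in the measured set?** The order is baseline PET, biopsy, therapy, repeat PET, second biopsy of the same site. Lesions are measured at both scans, limited only by size (1.5 cm) and number (10). No sentence says outright that the biopsied lesion is kept. This follows from the reference to all lesions and the absence of an exclusion.

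**Step 3: how far an artefact would carry.** Let a be the shift in the sampled lesion's percent change due to sampling, k the number of equally weighted sites, and f the share of patients biopsied between scans.

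- Patient-level shift = a/k.
- Shift in the group mean = f × a/k.

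The documents give none of a, k or f, and 6.14.1 does not define how site values combine into a patient's percent change. All are assumptions here: k = 3, f = 0.5 or 0.25, and a from 0 to 30 points in the direction of lower FES. The tested change is taken to be a decline.

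**Step 4: effect on the one-sided test against 20%, when the true change is exactly 20%** (noncentral t, n = 20, SD held at 25, noncentrality = group shift/5.59):

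| a (points) | Patient shift, k = 3 | Group shift, f = 0.5 | Rejection probability | Group shift, f = 0.25 | Rejection probability |
|---|---|---|---|---|---|
| 0 | 0 | 0 | 0.050 | 0 | 0.050 |
| 5 | 1.67 | 0.83 | 0.067 | 0.42 | 0.058 |
| 10 | 3.33 | 1.67 | 0.087 | 0.83 | 0.067 |
| 20 | 6.67 | 3.33 | 0.142 | 1.67 | 0.087 |
| 30 | 10 | 5.0 | 0.217 | 2.5 | 0.112 |

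Shifting only some patients also adds variance. At a = 30 and f = 0.5, SD = √(25² + 10² × 0.5 × 0.5) = 25.5 and the probability is 0.212, so the range barely moves.

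**Step 5: dependence on the number of sites.** With k = 10, f = 0.5 and a = 30, the group shift is 0.5 × 30/10 = 1.5 points and the probability is 0.083. With k = 1 in every patient, it is 15 points. The SD then becomes √(25² + 30² × 0.5 × 0.5) = 29.2, and the probability is 0.72 (0.83 if the added variance is ignored). An artefact in the other direction makes the test against 20% conservative and costs power instead: with a 5-point shift, power at a true 40% falls from 0.964 to 0.827 (noncentral t).

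**The case against.** The strongest objection is that the harm is assumed. A reader might infer from the sequence that the FES or FDG change in biopsied patients is biased. The documents do not support that: they say nothing on whether sampling alters uptake of either tracer, and zero is a legitimate value in the range. This stands, and it limits the point to a gap in the plan.

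A reader might also infer that false-positive rates of 0.7 or 0.8 are in prospect. Those need every patient to have a single site, half to be biopsied, a 30-point artefact, and an FES-lowering direction, all at once. Biopsy is optional, restricted to metastatic or recurrent disease, and may be replaced by an earlier sample. Section 6.10.2.c also places the FES regions on the three planes of highest uptake, which may limit sensitivity to a small sampled area. These large figures should not be relied on.

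A local tissue reaction showing up in maximum FDG SUV is a tempting mechanism, but it is not in the documents, and the test in 6.14.1 is of FES. Nor does the point cover all biopsied patients. It does not apply to substituted biopsies, and its FDG part does not apply where repeat FDG is omitted on SERD therapy. Section 6.10.3 says patients will already have had a clinical biopsy of the primary tumor and/or a metastasis, so the lesion need not be untouched at baseline.

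Finally, SUVs are recorded per site and 6.14.1 is worded permissively, so the comparison could be run without amending the plan. That holds only if the biopsied site is identified in the data, and naming the analysis in advance avoids choosing lesions after seeing results.

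**Conclusion.** The point holds in a limited form. For patients with the study's own baseline biopsy, a lesion that meets the size and number limits is sampled between the compared scans and remains in the patient average, and no planned analysis leaves it out. Any sampling effect would be attributed to therapy. Its existence, size and direction are unknown from the documents.

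For scale only, with 3 equally weighted sites, n = 20, SD 25 and an assumed FES-lowering artefact of 0 to 30 points, the group mean shifts by 0 to 5 points if half are biopsied. The nominal 0.05 test then rejects with probability 0.05 to 0.22 (0.05 to 0.11 if a quarter are biopsied). The effect is small with many sites and matters most with one or few. This is a low-cost improvement to the analysis and does not undermine the design.

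**What to change.** Record which site was biopsied and the biopsy date. In 6.10.2.c and 6.14.1, prespecify one sensitivity analysis: for patients biopsied between the scans, the patient-level FES change (and FDG change where FDG is repeated) recalculated without the biopsied site, whenever another quantifiable site exists. Keep that site in the primary summary and in the tissue-imaging correlation. Flag patients whose only site was biopsied, because this analysis cannot remove an effect in them.

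The cost is two recorded items and one extra analysis of SUVs already collected, with one site fewer for biopsied patients in that analysis. No scan, biopsy or treatment changes.

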### **6.6.3 General Concomitant Medication and Supportive Care Guidelines**

Because there is unlikely to be interaction of < 5 µg of [F]FES with other concomitantly administered drugs through the cytochrome P450 system, this section is not applicable.

The infusion and imaging procedure will be terminated in any patient who exhibits adverse reactions as described in section 6.6.1 and 6.8.1.

### **6.6.4 Duration of Therapy**

As this is an observational study, the results of [F]FES PETs and repeat FDG PETs are not used to direct therapy, and the duration of therapy is determined on the basis of clinical grounds by the referring physician, and is not influenced by the FES study.

### **6.6.5 Duration of Follow Up**

Patients will be followed up to 20 years after [F]FES PET. Patients removed from study for unacceptable adverse events will be followed until resolution or stabilization of the adverse event.

## **6.7 DOSING DELAYS/DOSE MODIFICATIONS**

As this is a trial of a diagnostic imaging agent to be administered before endocrine therapy, dosing delays and dose modifications are not relevant to this protocol.

## **6.8 ADVERSE EVENTS: LIST AND REPORTING GUIDELINE**

### **6.8.1 Adverse Events and Potential Risks**

No adverse events have been reported for diagnostic [F]FES administration at the strength described for this study in 267 patients studied at the University of Washington. Thus no adverse effects are expected as a result of the administration of [F]FES. The [F]FES dose is less than 0.002 of the recommended safe oral dose assuming an oral conjugated

estrogen dose of 2.5 mg in one day. Unexpected but potential adverse effects are listed below.

Anaphylaxis, Hypotension, Dyspnea, Chest pain, Flushing, Euphoria  
Infection at the injection site or systemic infection  
Extravasation of the dose

## 6.8.2 Adverse Events Characterization

6.8.2.1 the general definitions for adverse events are:

Adverse Event: Any unfavorable and unintended sign (including an abnormal laboratory finding), symptom, or disease temporally associated with the use of a medical treatment or procedure regardless of whether it is considered related to the medical treatment or procedure (attribution of unrelated, unlikely, possible, probable, or definite). Each AE is a unique representation of a specific event used for medical documentation and scientific analysis.

Serious Adverse Event (SAE): An SAE is defined in the FDA CFR 312 as any adverse drug experience occurring at any dose that results in any of the following outcomes: death, a life-threatening adverse drug experience, inpatient hospitalization, or prolongation of existing hospitalization, a persistent or significant disability/incapacity, or a congenital anomaly/birth defect. Important medical events that may not result in death, be life threatening, or require hospitalization may be considered a serious adverse drug experience when, based upon medical judgment, they may jeopardize the patient or subject and may require medical or surgical intervention to prevent one of the outcomes listed in this definition. We will report serious AEs via expedited reporting to FDA and to our local IRB.

Life-Threatening Adverse Event: Any adverse drug experience that places the patient or subject, in the view of the investigator, at immediate risk of death from the reaction as it occurred, i.e., it does not include a reaction that, had it occurred in a more severe form, might have caused death. AEs can be 'Unexpected' or 'Expected' for expedited reporting purposes only. A list of adverse events that have occurred or might occur (Reported Adverse Events and Potential Risks) can be found in Section 6.8.1.

In addition to oversight by the PIs, this study will be monitored by the UW/FHCRC Cancer Consortium Institutional Review Board and the Radiation Safety Committee.

